## 14.3.7 Analysis of exploratory efficacy endpoints

## **Binary endpoints**

The endpoints

- Having a decrease in EASI of at least 50% (EASI 50) from baseline to week 1, 2, 4, 6, 8, 12, and 16, assessed separately.
- Having a decrease in EASI of at least 75% (EASI 75) from baseline to week 1, 2, 4, 6, 8, 12, and 16, assessed separately.
- Having a decrease in EASI of at least 90% (EASI 90) from baseline to week 1, 2, 4, 6, 8, 12, and 16, assessed separately.
- Having vIGA-AD score of 0 (clear) or 1 (almost clear) at week 1, 2, 4, 6, 8, 12, and 16, assessed separately.

will be analysed on the full analysis set by computing frequency tables for each time point by treatment group.

Proportions with respect to these endpoints will be plotted by treatment group.

#### **Continuous endpoints**

The endpoints

- Change in EASI score from baseline to week 1, 2, 4, 6, 8, 12, and 16.
- Change in Worst Daily Pruritus NRS (weekly average) from baseline to weeks 1, 2, 4, 6, 8, 12, and 16.

will be analysed on the full analysis set by computing descriptive summary statistics for each time point by treatment group.

Individual and mean data as well as boxplots with respect to these endpoints will be plotted by treatment group.

Page 97 of 129

## 14.3.8 Pharmacodynamics analysis

For the following endpoints;

- Change in expression of AD disease biomarkers in serum from baseline to week 1, 4, and 16.
- Change in expression of AD disease biomarkers in skin biopsies from baseline to week 1, 4, and 16.
- Change in expression of AD disease biomarkers in skin tape strips from baseline to week 1, 4, and 16.

explorative analyses will be performed for the total population.

A summary of the results will be included in the CTR if the results are available in time for this. The full set of biomarker results will be reported in an addendum to the CTR.

## 14.3.9 Safety analysis

The analysis of safety will be based on the safety analysis set.

#### 14.3.9.1 Adverse events

AEs will be coded during the course of the trial according to Medical Dictionary for Regulatory Activities (MedDRA). AEs will be presented by preferred term and primary system organ class (SOC).

Treatment-emergent AEs will be summarised; however, all AEs recorded during the course of the trial will be included in subject data listings. The tabulations described in the following will only include the treatment-emergent AEs. In each of the tabulations, AEs are defined by MedDRA preferred terms within primary SOC.

AEs will be summarised in terms of the number of subjects with at least 1 event, the percentage of subjects with at least 1 event, the number of events, and the event rate per 100 patient years of observation time.

Related AEs are defined as AEs for which the investigator has not described the causal relationship to IMP as 'not related'.

An overall summary of the number of events and the number (percentage) of subjects with any treatment-emergent AEs, deaths, SAEs, permanent discontinuations from IMP, and/or withdrawals from the trial due to AEs, treatment-related AEs, mild and moderate AEs, and severe AEs will be presented.

Tabulations by SOC and preferred term will be presented for all AEs, SAEs, related AEs, and AEs leading to withdrawal from trial and/or permanent discontinuation of IMP. In addition, all AEs will be presented by severity and causal relationship to IMP, respectively.

The number of AEs and number of subjects with each type of AEs will be tabulated by treatment group from baseline to week 16, from baseline to week 32, and from week 17 to week 32.

AEs leading to withdrawal from trial and/or permanent discontinuation of IMP will be tabulated and listed. The detailed listing will provide an overview of the individual cases and include the age and sex of the subject, treatment received at the time of AE onset, the AE preferred and reported terms, causality and severity of the AE, the action taken with the IMP, AE outcome, start and stop date of AE, duration of AE, and number of days since first and last IMP administration. No narratives will be given.

SAEs will be evaluated separately, and a narrative will be given.

## 14.3.9.2 Vital signs and physical examination

The change in vital signs (blood pressure, pulse, and body temperature) from baseline to each relevant visit will be summarized by treatment group as mean, standard deviation (SD), median, minimum and maximum values for the safety analysis set.

Subjects with abnormal, clinically significant physical findings will be listed. Furthermore, a shift table for physical findings showing the change from baseline to week 16 in clinical assessments (normal; abnormal, not clinically significant; abnormal, clinically significant) will be performed.

#### 14.3.9.3 ECG

The change in ECG from baseline to each visit will be summarized by treatment group as mean, SD, median, minimum and maximum values for the safety analysis set.

Subjects with abnormal, clinically significant ECG will be listed. Furthermore, a shift table for ECG showing the change from baseline to week 16 in clinical assessments (normal; abnormal, not clinically significant; abnormal, clinically significant) will be performed.

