#### 10.2 Reasons for discontinuation of IMP

### 10.2.1 Reasons for permanent discontinuation of IMP

Subjects will permanently discontinue IMP in the event of:

- Withdrawal by subject
- An AE that, in the opinion of the investigator or sponsor's medical expert, contraindicates further dosing.
- Confirmed clinically significantly abnormal ECG or change in ECG.
- Initiation of prohibited medication which cannot be safely replaced by other non-prohibited medications.
- Evidence of pregnancy, or if the subject is noncompliant with the contraception requirements (see Section 8.2).
- Symptomatic infection with SARS-CoV-2 that is likely to have an impact on efficacy or safety data (i.e., patients with a SARS-CoV-2 infection without or very mild symptoms only (e.g., rhinitis or sore throat) might continue with the study at investigator's discretion and in accordance with the applicable local regulations)..
- Other reasons, at the discretion of the investigator. If other, a specification should be provided.

Page 66 of 129

It is not allowed to restart IMP treatment after discontinuation of IMP.

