### 10.3 Early termination assessments

#### Permanent discontinuation of IMP

Subjects who permanently discontinue IMP for any reason will be asked to attend an early termination visit as soon as possible after last administration of IMP and return to the trial site for additional visits as indicated below:

- An early IMP termination visit as soon as possible after last dose of IMP (in case of early termination before week 4: a nominal week 4 visit)
- An end of trial visit (safety follow-up visit 16 weeks after last administration of IMP).

See the schedule of trial procedures (Section 4) for data to be collected at these visits. The subjects will be asked to complete the diary until end of trial visit. The investigator will review any AEs which will be followed up according to Section 13.7, if the subject agrees.

Details on data to be recorded in the eCRF for subjects who permanently discontinue IMP can be found in Section 11.8.

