## 11.4.4 Electrocardiography

ECGs must be measured according to the schedule of trial procedures in (Section 4). At an unscheduled visit, it will be at the discretion of the investigator if an ECG should be measured.

At the respective visit, the individual measurements as well as the average of 3 consecutive 12-lead resting digital ECG will be recorded after the subject has been in supine position for at least 5 minutes. ECGs must be measured before any blood samples scheduled at the same visit.

A pre-evaluation of the ECGs will be performed by the investigator to evaluate immediate subject safety. At a minimum, the date of ECG pre-evaluation will be recorded in the source documents. In case of a suspected abnormal ECG, the investigator must take appropriate action, at their discretion.

The ECG data will be transferred to a central ECG service company for central evaluation. A cardiologist at the ECG service company will analyse and interpret the ECG data. The ECG service company will provide ECG evaluation reports to the trial sites.

The investigator must evaluate all abnormal ECG results ('clinically significant' or 'not clinically significant') and sign and date. The investigator is responsible for taking the final decision about the clinical significance of any abnormal ECG.

If a result is abnormal at the screening or baseline visit and considered by the investigator to be clinically significant, it will be up to the investigator's discretion to decide if the subject should be enrolled into the trial (respecting exclusion criteria no. 21 and 31). If a subject with an abnormal and clinically significant ECG result is enrolled, the investigator should provide a justification in the medical record.

During the trial, if a subject presents with a clinically significant abnormal ECG or a clinically significant abnormal change in ECG from baseline, the ECG should be repeated. If the ECG or change in ECG is confirmed clinically significantly abnormal, the subject must permanently discontinue IMP, and be withdrawn from the trial.

Trial ID: LP0145-2274 Date: **04-Jan-2023** Version: 5.0 Page 76 of 129

The collection and transmission of ECG data will be described in a separate ECG manual.

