## 14.3.9.4 Clinical laboratory evaluation

The change in each of the laboratory parameters from baseline to each visit will be summarized by treatment group as mean, SD, median, minimum and maximum values for the safety analysis set.

Laboratory parameters will be classified as 'low', 'normal', or 'high', depending on whether the value is below, within, or above the reference range, respectively. A shift table will be produced showing the categories at baseline against those at the end of treatment. Subjects with laboratory parameters outside the reference range will be listed.

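### The baseline-to-week-16 ECG shift table cannot show a clinically significant ECG first confirmed at week 4, 8 or 12, because those subjects are withdrawn

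*Combined protocol and SAP*

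**What the plan says.** Section 14.3.9.3 specifies one categorical ECG table, "a shift table for ECG showing the change from baseline to week 16 in clinical assessments", with three categories: normal; abnormal but not clinically significant; abnormal and clinically significant. The same section lists subjects with a clinically significant ECG and summarises ECG change at each visit by arm.

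Section 11.4.4 governs what happens when such an ECG occurs during the trial. For a clinically significant abnormal ECG or "clinically significant abnormal change in ECG from baseline, the ECG should be repeated". Then: "If the ECG or change in ECG is confirmed clinically significantly abnormal, the subject must permanently discontinue IMP, and be withdrawn from the trial". Section 10.2.1 also names "Confirmed clinically significantly abnormal ECG or change in ECG" among the reasons for permanently stopping IMP, but does not mention withdrawal from the trial.

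The two neighbouring safety sections also use a single end point. Section 14.3.9.2 plans "a shift table for physical findings showing the change from baseline to week 16 in clinical assessments", and 14.3.9.4 says "A shift table will be produced showing the categories at baseline against those at the end of treatment".

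**The concern.** The table has a column for clinically significant ECGs at week 16, but the protocol removes a subject from the visit schedule when that finding is confirmed earlier. Subjects are then missing from the table because of the outcome it is meant to count.

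Safety of LEO 138559 is the secondary objective. Section 12.2 gives a specific reason for collecting ECGs, namely possible indirect cardiac effects of large proteins with long exposure. No formal tests are planned and the arms are planned at 8 and 4 subjects, so readers will rely on the by-arm descriptive tables. One omitted subject visibly changes such a table.

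**Working it through.** The plan states no figure to reproduce here, and the sample size is not power-based. The check is of logic first, then of size.

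**Step 1: the visits.** From Panel 2, ECGs after baseline and up to the end of treatment are at weeks 4, 8, 12 and 16, which is 4 visits. A further ECG is at week 32, and ECGs are possible at early-termination and unscheduled visits.

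**Step 2: whether a removed subject can have a week 16 ECG.** Under 10.3, a subject withdrawn from the trial is asked to attend an early-termination visit only. A subject who stops IMP but stays in follow-up has the early-termination visit and "An end of trial visit (safety follow-up visit 16 weeks after last administration of IMP"). The timing of that last visit depends on whether the dose due on the day of the ECG was given (both cases shown):

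| First confirmed at | Last dose | End-of-trial visit (last dose + 16 weeks) |
|---|---|---|
| Week 4 | Week 2 or 4 | Week 18 or 20 |
| Week 8 | Week 6 or 8 | Week 22 or 24 |
| Week 12 | Week 10 or 12 | Week 26 or 28 |

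None falls at week 16 (window ±3 days), so neither route supplies a week 16 ECG.

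**Step 3: whether another rule fills the gap.** Section 14.3.12 uses observed cases for by-visit tables and reports the number of subjects without data. Section 14.3.13 defers missing-value handling to the SAP. Nothing in the text available assigns an early-termination ECG to week 16.

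**Step 4: size.** With first confirmation equally likely at each of the 4 visits (assumption), 3/4 = 75% of confirmed cases cannot appear and 1/4 = 25% can.

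As a sensitivity check, let h be a constant risk of first confirmation at each visit (assumption, shown as a range), with no other dropout and independent subjects:

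- any confirmed case by week 16: 1 − (1 − h)^4
- first confirmed at week 16, so visible: h(1 − h)^3
- share visible: the second divided by the first
- at least one case among 12 subjects: 1 − (1 − p)^12, with p set to each probability in turn

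| h | Any by week 16 | First at week 16 | Share visible | At least 1 of 12: any visit | At least 1 of 12: week 16 only |
|---|---|---|---|---|---|
| 0.01 | 3.9% | 1.0% | 24.6% | 0.38 | 0.11 |
| 0.025 | 9.6% | 2.3% | 24.1% | 0.70 | 0.25 |
| 0.05 | 18.6% | 4.3% | 23.1% | 0.92 | 0.41 |
| 0.10 | 34.4% | 7.3% | 21.2% | 0.99 | 0.60 |

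**Step 5: an example.** Suppose one of 8 LEO 138559 subjects is confirmed at week 8 and the other 7 complete without such a finding. The true count is 1/8 = 12.5%, and the week 16 table shows 0/7.

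**Step 6: the other two tables.** The physical-examination shift uses 1 of 4 post-baseline visits up to week 16 (weeks 4, 8, 12, 16). The chemistry and haematology shift uses 1 of 5 (weeks 2, 4, 8, 12, 16) if end of treatment means week 16, as Panel 2 labels it. Sections 11.4.2 and 11.4.5.2 leave action on a clinically significant finding to the investigator and do not require withdrawal. A persistent change in a subject who attends week 16 is therefore seen, and one that resolves earlier is missed.

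**The case against.** The strongest reply is that nothing is hidden. Section 14.3.9.3 lists every subject with a clinically significant ECG. Section 11.4.4 makes new clinically significant findings after randomisation reportable as adverse events. Section 14.3.9.1 tabulates adverse events by arm for three periods, and separately tabulates and lists those leading to withdrawal or to stopping IMP. The secondary endpoint is the number of treatment-emergent adverse events, not ECG shifts. By-visit ECG and laboratory summaries give minimum and maximum, which with 8 and 4 subjects show individual extremes. All of this stands, and it limits the consequence. It does not repair the shift table: adverse event tables are organised by preferred term rather than ECG category, numerical summaries do not show category shifts, and a listing is not a by-arm summary.

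The 75% rests on uniform first confirmation, whereas the rationale in 12.2 concerns long exposure. If cases cluster late, more would be visible. That stands, and the percentage should be read as illustrative.

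The SAP is to be finalised before unblinding and could add a rule for early-termination ECGs. That is possible, and it is the natural place for the fix.

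A single worst-category table running to week 32 would mix treatment with 16 weeks off drug, a period in which Panel 5 allows systemic corticosteroids if medically needed. That is a fair objection, so the two periods should be kept apart.

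**Conclusion.** The point holds for one column of one table. As written, the ECG shift table omits clinically significant cases first confirmed at 3 of the 4 scheduled on-treatment ECG visits. Between 21% and 25% of such cases would be visible under the constant-risk assumption with h from 0.01 to 0.10. The conclusion assumes that 11.4.4 or 10.2.1 is followed and that no later SAP rule carries an early-termination ECG into week 16. It is a modest and cheap improvement.

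Three stronger readings are not supported:

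- A reader might infer that the table will look clean whatever the drug does. It will not: shifts to abnormal but not clinically significant remain, as do cases first confirmed at week 16, including those arising after the week 12 ECG. Findings not confirmed on repeat do not trigger removal.
- A reader might infer that the physical-examination and laboratory tables have the same defect. They lack the mandatory withdrawal rule. For the laboratory table, the text does not settle whether end of treatment includes early-termination values: Panel 2 labels week 16, but 11.6.3 pairs the end-of-treatment visit with the early-termination visit for biopsies.
- A reader might infer that week 32 data go unused. That is true only of the shift tables, because the by-visit summaries cover week 32 for ECG and laboratory values.

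**What to change.** In 14.3.9.3, and for consistency in 14.3.9.2 and 14.3.9.4:

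1. Add a by-arm shift from baseline to the worst post-baseline category during the treatment period, using scheduled, unscheduled and early-termination assessments. For laboratory parameters give worst-low and worst-high separately.
2. Keep the week 16 shift as a secondary table, and state whether the laboratory end of treatment includes early-termination values.
3. Report the period to week 32 separately, matching the adverse event windows in 14.3.9.1.
4. State how a clinically significant ECG that is not confirmed on repeat is classified, since a worst-category rule would otherwise pick it up.

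The cost is SAP wording and one extra set of tables, with no new data. The downside is that unscheduled assessments are made at the investigator's discretion, so subjects may be assessed unequally. A footnote giving the number of assessments per arm would disclose this.

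Separately, 10.2.1 (stop IMP) and 11.4.4 (stop IMP and be withdrawn) differ on whether the subject stays in follow-up, and must be reconciled. The table changes above work under either.

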## 14.3.9.4 Clinical laboratory evaluation

The change in each of the laboratory parameters from baseline to each visit will be summarized by treatment group as mean, SD, median, minimum and maximum values for the safety analysis set.

Laboratory parameters will be classified as 'low', 'normal', or 'high', depending on whether the value is below, within, or above the reference range, respectively. A shift table will be produced showing the categories at baseline against those at the end of treatment. Subjects with laboratory parameters outside the reference range will be listed.

#### 14.3.9.5 Anti-drug antibodies

For the exploratory endpoint

• Having a positive ADA response at weeks 0, 4, 8, 12, 16, 32, assessed separately.

the ADA status (positive vs. negative) including actual ADA titre at each assessment time point will be summarised. If considered relevant, descriptive statistics including number of subjects, mean, SD, median, and range of the actual ADA titres and visit will be provided. The ADA status across the trial for each subject (positive vs. negative) will also be classified and summarised.

The association of ADA status across the trial (positive vs. negative) with AEs/SAEs may be evaluated. In addition, the association of ADA titres (≥ median titre in positive subjects versus < median titre) with AEs/SAEs may be evaluated for ADA positive treated subjects only. The ADA positive subjects across the trial may also be divided into persistent positive versus transient positive. A subject will be considered as persistent positive if he/she has positive ADA for at least 2 consecutive visits with ADA assessment. Otherwise, the subject will be considered as transient ADA positive. The associations between ADA and AEs/SAEs may be summarised for both persistent positive subjects versus transient positives subjects.

For subjects who develop ADA, the change in EASI at end of treatment will be listed.

For ADA, all subjects with titre information will be listed. Graphical presentations may be performed.

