#### **Pharmacokinetics**

Based on the human PK data from the FiH trial, the PK of LEO 138559 is as expected for a mAb (IgG1) directed toward a membrane-bound target, and the target-mediated drug disposition (TMDD) characteristics are also visible in the observed human data as it was in the cynomolgus data.

After SC administration, LEO 138559 is slowly absorbed with a mean time to maximum concentration of approximately 7.5 days. After multiple dosing, the elimination half-life was observed to be between 21–25 days. At and above the exposure level relevant for clinical testing (150 mg Q2W), the elimination is dominated by linear clearance and close to dose-proportionality is expected at steady state. The exposure at steady state following administration of 450 mg Q2W is expected to result in lower exposure than 450 mg every week for 5 weeks (the highest dose in the LP0145-1315 trial).

A detailed overview of clinical data on LEO 138559 is available in the current investigator's brochure [36].

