#### 11.4.6 Anti-drug antibodies measurements

Blood samples will be collected to determine ADA levels at pre-determined time points according to the schedule of trial procedures (Section 4). At an unscheduled visit, it will be at the discretion of the investigator if a blood sample to determine ADA levels should be collected. In case a blood sample for ADA levels determination is drawn, also a PK blood sample should be taken.

Serum samples for determination of presence or absence of ADA will be analysed by a laboratory using a validated bioanalytical method. A tiered testing scheme will be employed,

Page 80 of 129

with the first step being screening. Samples found positive in the screening step will be tested in the confirmatory step. Samples confirmed positive for ADA in the confirmatory step will undergo endpoint titre determination. Details of the analytical method used will be described in a bioanalytical report.

Collection, handling, and shipment instructions for ADA blood samples are provided in a laboratory manual.

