# 12 Scientific rationale for trial design and appropriateness of

# 12.1 Scientific rationale for trial design

assessments

LP0145-2274 is a randomized, double-blinded, active comparator-controlled, 16-week, single-site exploratory, mechanistic trial designed to evaluate the effect on the molecular signature of SC administered LEO 138559 450 mg Q2W compared with Dupixent® Q2W in adults with moderate to severe AD.

The primary endpoint is selected to gain information about the mode of action of LEO 138559 and the influence of blocking of IL-22 pathway on gene expression in lesional skin.

Based on PK, PD, and safety results of the FiM trial with LEO 138559 (LP0145-1315), the dose regimen LEO 138559 450 mg Q2W was selected for investigation in this trial. In addition to the Q2W dosing schedule, an additional dose of IMP will be given to the subjects at week 1 to reach steady state exposure early in the treatment period. According to a PK model developed based on preliminary data from the FiM trial, the additional dose given at week 1 should allow 75% of steady state exposure to be reached already after 3 weeks of treatment. The 16-week treatment period was selected to ensure sufficient time to evaluate the impact of LEO 138559 on disease severity as AD. Further, given the expected half-life, dosage, and dosing frequency of LEO 138559, it is expected that LEO 138559 achieve steady state concentration before the end of this period and a maximum therapeutic effect will be achieved by this time. A safety follow-up period of 16-week after last dose of IMP is considered an appropriate length as serum concentrations of LEO 138559 are expected to be declined to nondetectable levels (below the lower limit of quantification) in most subjects at that timepoint.

The use of Dupixent® as a comparator will serve as reference to evaluate the mode of action, efficacy and safety of LEO 138559. The comparison with an approved immunoregulatory agent that selectively and simultaneously inhibits IL-4 and IL-13 allows for an evaluation of similarity or differences in the mechanistic effect. Dupixent® will be administered according to the prescription instructions (standard of care) for adult subjects with moderate to severe AD with an initial dose of 600 mg followed by Q2W injections with 300 mg.

Trial ID: LP0145-2274 Date: **04-Jan-2023** 

Page 87 of 129

Version: 5.0

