#### 14.3.10 Pharmacokinetic analysis

The endpoint

• Serum concentration of LEO 138559 at weeks 0, 1, 4, 8, 12, 16, and 32, assessed separately.

will be evaluated based on the PK analysis set.

LEO 138559 serum concentrations will be listed and summarized by visit. The serum concentrations will be included in a cross-trial population PK analysis and reported separately.

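### ADA samples drawn on drug are classed as positive or negative with no inconclusive category, and the paired LEO 138559 concentration is not used to interpret a negative

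*Combined protocol and SAP*

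**What the plan says.** The endpoint in Section 14.3.9.5 is "Having a positive ADA response at weeks 0, 4, 8, 12, 16, 32, assessed separately". For it, "the ADA status (positive vs. negative) including actual ADA titre at each assessment time point will be summarised", and each subject also receives a positive or negative status across the trial. Titres come from positives only (Section 11.4.6): "Samples confirmed positive for ADA in the confirmatory step will undergo endpoint titre determination". Positives may optionally be split by duration: "A subject will be considered as persistent positive if he/she has positive ADA for at least 2 consecutive visits with ADA assessment"; all other positives are transient. ADA may be related to AEs and SAEs, and EASI change is listed for subjects who develop ADA.

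On the paired sample, Section 11.4.6 says "In case a blood sample for ADA levels determination is drawn, also a PK blood sample should be taken", and Panel 2 schedules PK at every ADA visit. Section 14.3.10 evaluates "Serum concentration of LEO 138559 at weeks 0, 1, 4, 8, 12, 16, and 32, assessed separately" by listing, by summary per visit, and in a separately reported population PK analysis. Neither 14.3.9.5 nor 14.3.10 links ADA to concentration. Section 11.4.6 calls the assay validated and leaves its details to a bioanalytical report.

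**The concern.** Circulating antibody drug can interfere with an ADA assay, so a negative reading with drug present may mean either no ADA or ADA that was not detected. The plan's two categories put both into negative. The concentration that would help to separate them is measured at the same visit, but no rule brings it in.

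Three results are exposed:

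- the ADA rates at weeks 4 to 16, which could be understated;
- the across-trial status of a subject with no sample after washout;
- the duration label of a subject whose ADA is first detected at week 32, who cannot have two consecutive positive visits and so becomes transient by rule.

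ADA sits under the secondary safety objective, and Section 12.2 gives evaluation of immunogenicity as the reason for collecting it. With 8 planned LEO subjects, one reclassified subject moves a rate by 1/8 = 12.5 percentage points.

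**Working it through.** **Inputs.**

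- Doses at weeks 0, 1, 2, 4, 6, 8, 10, 12 and 14, that is days 0, 7, 14, 28, ..., 98 after the first dose (Panel 2, Section 9.2).
- Half-life (Section 5.2): "the elimination half-life was observed to be between 21–25 days".
- Time to maximum about 7.5 days after SC dosing, with linear clearance dominating at the relevant exposure (Section 5.2).
- PK sampled before dosing (Section 11.5.1). The same timing for ADA is inferred from the pairing.
- 8 LEO subjects planned (Section 14.1).

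**Model.** One compartment with first-order absorption, summed over all doses d given before time t:

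C(t) ∝ Σ ka/(ka − ke) × [exp(−ke(t − d)) − exp(−ka(t − d))]

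Here ke = ln 2 / half-life, and ka is solved from ln(ka/ke)/(ka − ke) = 7.5 days. This gives ka of 0.346, 0.361 and 0.375 per day for half-lives of 21, 23 and 25 days.

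**The plan's own figure.** Section 12.1 expects 75% of steady-state exposure after 3 weeks. The sponsor's model and exposure metric are not given, so this can only be bracketed. Relative to the steady-state average, the model gives 67-75% for the mean over days 7-21, 78-88% for the mean over days 14-28, and 83-93% for the day-21 concentration. The stated 75% is compatible with this.

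**Concentration at each ADA visit, as a share of steady-state trough.**

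| Week | Half-life 21 d | 23 d | 25 d |
|---|---|---|---|
| 4 | 0.896 | 0.848 | 0.804 |
| 8 | 0.959 | 0.935 | 0.910 |
| 12 | 0.984 | 0.972 | 0.959 |
| 16 | 0.994 | 0.988 | 0.981 |
| 32 | 0.025 | 0.034 | 0.044 |

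An instantaneous-input variant agrees to within 0.001. Week 32 can be checked by hand: it is 112 days after week 16, so the share is the week-16 value times 2^(−112/half-life). That is 0.994 × 0.0248 = 0.025 at 21 days and 0.981 × 0.0448 = 0.044 at 25 days. It is also 126 days after the last dose, or 126/25 = 5.0 to 126/21 = 6.0 half-lives. This agrees in direction with Section 12.1, where by the end of follow-up "serum concentrations of LEO 138559 are expected to be declined to nondetectable levels" in most subjects. Target-mediated elimination, which the model omits, would lower week 32 further.

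**Counts.** Post-baseline samples in the LEO arm: 8 × 5 = 40. On drug: 8 × 4 = 32. After washout: 8 × 1 = 8. These assume no dropout and no missed sample.

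**Range of effect.** Masking depends on absolute concentration against the assay's drug tolerance, and neither is given. If tolerance exceeds the observed troughs, 0 of the 32 are in doubt. If it lies below about 80% of steady-state trough, all 32 could be, provided all read negative.

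**The case against.** Several points on the other side stand.

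- A reader might infer that on-treatment ADA results are in fact masked. The documents do not show this. The method is described as validated, and the percentages above show when drug is present, not that it interferes.
- A reader might infer that ADA is reported only as a dichotomy, or that the PK data go unused. Neither is so. Titres are reported, and concentrations are listed, summarised and modelled. With 8 subjects, a reader could match the two listings by hand. However, titres exist only for positives, and no rule acts on the match.
- Week 32 is a low-drug sample and is assessed separately, so a completer masked on treatment but still positive at week 32 would be seen. The protection is partial. ADA may wane by then. Under Section 10.3, subjects who withdraw from the trial are asked only for an early termination visit soon after the last dose, so they may have no washout sample. Those who stop IMP but stay in the trial are asked back 16 weeks after their last dose.
- The persistent/transient split and the AE associations are optional.
- Calculating rates among conclusive samples only would be a poor remedy. It drops on-drug negatives and keeps on-drug positives. For illustration, 1 positive and 7 inconclusive results would read as 1/1 = 100% rather than 1 of 8 tested.
- Section 14.3.12 has the SAP finalised before the code is broken, so it could supply this detail. But 14.3.9.5 already states a two-way classification, and a tolerance figure in the bioanalytical report would not change it.

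**Conclusion.** The point holds as a gap in classification and reporting, not as evidence of bias. Four of five planned post-baseline LEO-arm samples (up to 32 of 40) are taken at roughly 80-99% of steady-state trough, a negative among them is reported as negative without qualification, and the concentration drawn alongside is not used to interpret it. The number of results affected is unknown, between 0 and 32. The possible misclassification concerns on-treatment rates, subjects without a week-32 sample, and a subject positive only at week 32.

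The timing rests on linear one-compartment kinetics with the protocol's half-life and time to maximum. Week 4 is near steady state only approximately. The point does not concern the comparator arm, and the primary and secondary endpoints are untouched. Severity is low: the endpoint is exploratory, the trial is descriptive, and no formal tests are planned.

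**What to change.** In Section 14.3.9.5, or in the SAP before unblinding, state the assay's validated drug tolerance and then:

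1. List the paired LEO 138559 concentration beside ADA status and titre for each subject and visit.
2. Report each visit as positive, negative or inconclusive, where inconclusive means ADA-negative with a concentration above the tolerance. Give counts over all tested subjects, not a rate among conclusive samples.
3. For across-trial status, keep any confirmed positive as positive. Call a subject negative only if there is no positive and the last post-baseline sample (normally week 32) is a conclusive negative. Call all others inconclusive.
4. Report week 32 separately, and do not label a subject positive only at the last sample as transient.

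The cost is SAP wording and one listing; no new sample, visit or assay is needed. The downside is that the ADA-negative rate may look less favourable. If the tolerance exceeds the observed troughs, the visit-level classification does not change and the negatives become easier to defend.
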